9.5 Study Size

All patients registered in the PHARMO outpatient pharmacy database and meeting the inclusion criteria will be included. The size of the population receiving rivaroxaban will be dependent on market uptake across the indications of interest (DVT/PE treatment, ACS and SPAF).

According to a preliminary sample size calculation, based on an incidence of haemorrhagic stroke in vitamin K antagonist-treated patients of 5 per 1000 person-years, 12,000 rivaroxaban-treated patient-years and 48,000 vitamin K antagonist-treated patient-years would be required to exclude a 50% increased risk of haemorrhagic stroke in rivaroxaban-treated patients compared with vitamin K antagonist-treated patients with a power of 80%.

9.6 Data management

The PHARMO Database Network combines data from different sources (pharmacy, hospital, laboratory etc.). These different sources are probabilistically linked through validated algorithms that ensure the privacy of the patients is maintained. Before databases are linked, those patients for whom linkage-critical information (date of birth, gender, GP) is missing are removed.

For each study, specific checks on the linked data are performed, depending on which data sources are used. Patients are regarded eligible to be included in a study if they are registered and can be followed in all required databases. For the PHARMO pharmacy databases specifically, prescriptions that have not been dispensed (because patients did not collect them) are removed from the dataset. Furthermore, the prescribed dosage regimen and dispensed quantity are checked and extremely high dosages and quantities for the specific type of drug are regarded as missing values.

Study data are manipulated and analysed using the utility SAS Enterprise Guide, an environment for SAS enabling the storage of syntaxes or codes belonging to a single study in one project file, subdivided into project flows for different aspects of a study. All programming is developed in accordance with standard operating procedures and reviewed by an experienced analyst at PHARMO. Furthermore, all results and reports are audited by the Quality Control department, using a standardized check list.

9.7 Data analysis

The following analyses will be performed.

9.7.1 Patient characteristics and drug utilization

The overall patient populations will be described according to the descriptive variables mentioned in [Section 9.3.1](#), and stratified by naïve or non-naïve status, and switching status.

The patient populations, stratified by indication (VTE prevention, DVT/PE treatment, SPAF, ACS, other), will be described according to the descriptive variables. Where information from hospital admissions or GP notes are not available, the diagnosis associated with the prescribing of rivaroxaban will be assigned to one of the indications based on the dose and duration of treatment (see [Section 7](#)).

The baseline risk of being dispensed one of the co-medications or being hospitalized for bleeding prior to the index date will be assessed by computing the odds ratio of being dispensed that drug or being hospitalized for that indication among first-time users of rivaroxaban compared with first-time users of standard of care. Age- and sex- adjusted odds ratios and 95% confidence intervals will be computed using logistic regression models both overall and stratified by indication. Cohorts will be stratified based on naïve or non-naïve status, and switching status within the non-naïve group.

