- The prevention of venous thromboembolism (VTE) in adult patients undergoing elective hip or knee replacement surgery (recommended dose: 10 mg rivaroxaban od for 35 days following hip replacement surgery and 14 days following knee replacement surgery).
- Co-administered with acetylsalicylic acid (ASA) alone or with ASA plus clopidogrel or ticlopidine, for the prevention of atherothrombotic events in adult patients after an acute coronary syndrome (ACS) with elevated cardiac biomarkers (recommended dose 2.5 mg bid).

As is the case with other anticoagulants, clinical studies of rivaroxaban have identified haemorrhage as an important safety outcome ([Lassen et al. 2008](#); [Turpie et al. 2009](#)). A post-authorization safety study programme is planned for several European countries. The aim of this document is to summarize the design of a population-based study to characterise new users of rivaroxaban, assess patterns of drug utilization, including adherence to label recommendations, and to assess the risk of bleeding associated with rivaroxaban treatment in comparison with treatment with standard of care, in routine clinical practice in the Netherlands, for DVT/PE treatment, SPAF and ACS. For DVT/PE treatment and SPAF, standard of care is treatment with a vitamin K antagonist (acenocoumarol or phenprocoumon), and for the secondary prevention of ACS, standard of care is antiplatelet drug(s) such as low-dose acetylsalicylic acid, clopidogrel, dipyridamole, prasugrel, ticlopidine and ticagrelor. The standard of care treatments for ACS will require at least dual antiplatelet and be analysed as combination treatment, irrespective of the individual drug combinations used.

8 Research questions and objectives

This post-authorization study was designed to assess patient characteristics and patterns of drug utilization and to quantify outcomes related to safety and effectiveness in new users of rivaroxaban compared with new users of standard of care.

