9.2 Setting

Study drug users will be selected from the outpatient pharmacy database. This database records all outpatient dispensings from primary and secondary care in a well-defined geographic area. All study drug users living in this area will be captured in the database. All patients aged 2 years and above who have been registered in the database for at least 1 year before the index date will be included. A sub-population will be defined of patients for whom GP recorded information is also available.

The enrolment period will start on December 10, 2011 (the day after rivaroxaban received first marketing authorization in the Netherlands for the ‘treatment of DVT and long-term secondary prevention of recurrent DVT and PE’). End of enrolment will be 31 December 2017 and end of follow-up will be 31 December 2018. Interim reports will be provided for data collected 2 and 4 years after the date that rivaroxaban receives reimbursement approval for DVT treatment (see [Section 6](#) for detailed milestones). The characteristics of the two study cohorts in the first year and subsequent years of the enrolment period will be compared.

The drug utilization analysis ([Section 8.1.1](#)) will be performed in the sub-population captured by both the outpatient pharmacy database and the GP database, in order to enrich the data for the assignment of indication of use.

The Adverse Outcomes analysis (Sections [8.1.2](#) and [8.2](#)) will be performed in the full rivaroxaban cohort (outpatient pharmacy database with outcomes available from Medical Register), using the dosing as a proxy for the indication when this information is not available, and in the subcohort of comparator drug users captured by both the outpatient pharmacy database and the GP database.

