9.3 Variables

9.3.1 Patient characteristics and drug utilization

Descriptive variables of drug utilization will be presented only for the subpopulation captured by both the outpatient pharmacy database and the GP database, as only in this subpopulation sufficient information for the assignment of the indication of use is available. The following characteristics, including risk factors/potential confounders for the outcomes under study, will be presented for comparison between the two cohorts:

- age and sex distribution at index date 
- dose of index drug at index date (not available for vitamin K antagonists as dosing is determined in anticoagulation clinics) 

- dispensed amount (can be used to estimate duration of treatment) ✓
- where available based on hospital discharge diagnosis or from available GP notes, diagnosis associated with the prescribing of the index drug (where not available, dose and duration of index drug will be used as a proxy for the associated diagnosis among rivaroxaban users). Hospital discharge diagnoses and procedures will be identified within 4 weeks before until 7 days after the index date and GP diagnosed will be identified during the index month or in the month before the index date.
- proportion of patients defined as naïve, non-naïve, recent switchers and distant switchers ✓
- number of pregnant women at index date (if communicated by midwife or gynaecologist) ✓
- number of pregnancies after index date (if communicated by midwife or gynaecologist) ✓
- type of other anticoagulant use before the index date among the non-naïve group ✓
- use of specific prescribed medications both in the year before the index date and following the index date, confirming the ACS indication: antiplatelet drugs (low-dose acetylsalicylic acid, clopidogrel, dipyridamole, prasugrel, ticlopidine and ticagrelor); ✓

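### Rivaroxaban users without a recorded diagnosis get their indication from dose and duration, and dose and duration are then reported by that indication, which tilts these tables towards agreement with the label

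*Protocol*

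**What the plan says.** Indication for rivaroxaban is taken first from hospital discharge diagnoses or GP records. Section 9.3.1 sets the windows: hospital diagnoses "will be identified within 4 weeks before until 7 days after the index date", and GP diagnoses from the index month or the month before.

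Where neither source yields a diagnosis, 9.3.1 states that "dose and duration of index drug will be used as a proxy for the associated diagnosis among rivaroxaban users". Section 9.7.1 gives the same fallback: "Where information from hospital admissions or GP notes are not available", the patient "will be assigned to one of the indications based on the dose and duration of treatment", with a pointer to Section 7, where the label regimens are listed.

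Section 9.7.1 then says that the populations, "stratified by indication (VTE prevention, DVT/PE treatment, SPAF, ACS, other), will be described according to the descriptive variables". The descriptive variables in 9.3.1 include "dose of index drug at index date" and the dispensed amount, which 9.3.1 says can be used to estimate treatment duration.

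Section 8.1.1 makes dose and duration of rivaroxaban use part of the primary objective; the abstract adds indication. Section 7 states that the study is to "assess patterns of drug utilization, including adherence to label recommendations".

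**The concern.** A table of dose and duration by indication is informative only if indication was established independently of dose and duration. For proxy-assigned patients it was not. They are in a stratum because their regimen resembles the one listed for it, so finding that they resemble it says nothing about practice.

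Take a patient treated for atrial fibrillation with no diagnosis in the window, dispensed 10 mg once daily. Of the regimens listed in Section 7, this matches the one for VTE prevention. Under the rule the patient would be counted there, and the departure from the regimen listed for SPAF would not appear in any table.

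At stake is the description of real-world dosing within each indication. Departures from the label would be understated in the strata where a regulator would look for them.

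**Working it through.** The protocol gives no figure for the share of patients assigned by proxy or for expected label concordance, so there is no figure of its own to reproduce. The study-size calculation in 9.5 concerns haemorrhagic stroke and has no bearing here. The check is a reading of the rule, followed by a bounding calculation.

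**Step 1: is the rule circular?**

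- Stratum definition (9.3.1, 9.7.1): dose and duration matched to Section 7.
- Reported within the stratum (9.7.1 with 9.3.1): index dose and dispensed amount, the source for duration.

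For proxy-assigned patients the two sets coincide. Section 9.7.1 does not keep these patients apart from those with a recorded diagnosis.

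**Step 2: whom does it affect?** Only rivaroxaban users without a diagnosis, and only the tables stratified by indication. Section 9.7.1 also describes the overall populations on the same variables, and those tables do not use the proxy. The drug-utilization analysis is confined to patients in both the pharmacy and GP databases (9.2, 9.3.1), which should make q smaller. It need not make it zero. The diagnosis windows are short, so a patient diagnosed earlier, such as one switching from a vitamin K antagonist, may have no diagnosis inside them. The fallback is also written into the sections that govern this GP-linked analysis.

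**Step 3: how large could it be?** Assumptions, none from the protocol:

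- a = true label concordance, taken as equal in diagnosed and proxy-assigned patients;
- q = share of the tabulated patients assigned by proxy;
- every proxy-assigned patient appears concordant.

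Reported concordance = (1 − q) × a + q × 100%. The excess over the truth is q × (100% − a).

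For a = 80%:

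- q = 10%: 0.9 × 80% + 10% = 82%
- q = 30%: 0.7 × 80% + 30% = 86%
- q = 50%: 0.5 × 80% + 50% = 90%

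| Assumed true concordance | q = 10% | q = 30% | q = 50% |
|---|---|---|---|
| 70% | 73% | 79% | 85% |
| 80% | 82% | 86% | 90% |
| 90% | 91% | 93% | 95% |

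With a = 80%, apparent discordance falls from 20% to 18%, 14% or 10%.

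**Step 4: why this is an upper bound.** The list of indications includes an *other* group, so a regimen that fits nothing in Section 7 need not be forced into a labelled stratum. The regimens also overlap: 20 mg once daily is listed for SPAF and for continued DVT/PE treatment. Matching is therefore not one-to-one, and a patient may fit the assigned regimen only in part. The *other* group does not remove the bias, because patients sent there leave the denominators of the labelled indications.

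**Step 5: is duration known at index?** The protocol does not say whether duration means days supplied at the first dispensing or total time on treatment. Section 9.6 shows that the dosage regimen and dispensed quantity are held with the pharmacy data, so the former could be calculated at index. Realised duration is post-index and can be cut short by bleeding, death or stopping.

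**The case against.** The best defence is that the proxy is a fallback, used only after hospital and GP sources fail, in a subpopulation chosen to enrich the information on indication. Section 8.1.1 asks for dose and duration without naming indication, and the overall tables answer that without the proxy. Label adherence appears as one aim in Section 7, and 9.7.1 defines no adherence measure. Both a and q in the calculation are assumed. One could add that separating two groups in a table is commonly left to the SAP.

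Most of this stands as a limit on scope and size. It does not remove the circularity, because the protocol itself fixes both the assignment rule and the description by the assigned indication.

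A reader might infer two stronger points that the protocol does not support:

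- **That the proxy rules contradict each other.** Sections 9.2 and 9.4 refer to dosing only ("using the dosing as a proxy for the indication when this information is not available"), whereas 9.3.1 and 9.7.1 refer to dose and duration. The former describe the adverse outcomes analysis in the full rivaroxaban cohort; the latter describe drug utilization in the GP-linked subpopulation. They are different rules for different analyses.
- **That rivaroxaban patients who stop early are moved between indication groups in the outcome analysis.** This would require treatment duration to enter the proxy there, and 9.2 and 9.4 do not say that it does.

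**Conclusion.** The point holds for dose and duration described by indication in the drug-utilization analysis. In proxy-assigned rivaroxaban users these results are partly self-defined and lean towards the label. Any label-adherence reading of the same tables inherits the bias; that such a reading will be made by indication is inferred from the Section 7 aim together with the stratification in 9.7.1.

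The size cannot be determined from the protocol because q is not given. With a = 80%, the overstatement is at most 2, 6 or 10 percentage points at q = 10%, 30% or 50%. These are bounds on assumed inputs and should not be read as estimates. Use of post-index information is a possibility left open by the undefined term, not an established fact.

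A correction is worth making because the bias lies in a primary descriptive objective and is cheap to avoid.

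**What to change.** In 9.7.1, state that dose, duration and label adherence by indication will be reported only for patients with a recorded hospital or GP diagnosis, and that rivaroxaban users assigned by proxy will be shown in a separate table. That table also makes q visible.

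In 9.3.1 and 9.7.1, define duration as used in the proxy. If it is kept, limit it to days supplied at the index dispensing. Removing duration altogether is not required: it would avoid the post-index question but might discard information that helps to separate regimens.

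The cost is a few sentences, one extra table and smaller indication-specific tables. No new data are needed, and no dose or treatment rule changes.

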9.7.2 Safety and effectiveness outcomes

The two cohorts (of first-time users of rivaroxaban and first-time users of standard of care) will be followed up from the index date until 12 months after the end of the enrolment period for potential outcomes (safety and effectiveness). For each outcome, the first hospitalization for that outcome during the follow-up period will be identified. A separate follow-up will be performed for each of the outcomes.

For all outcomes (for DVT/PE treatment, SPAF and ACS), crude incidence rates will be estimated in both cohorts, using an as-treated approach. In this, person–time will be categorized into current, recent, past and non use. Current use will refer to person–time up to 7 days after the end of supply of the index drug, recent use will refer to person–time up to 90 days after the end of current use, past use will include all person–time contribution after the end of recent use up to 1 year after the end of current use, non-use will include all remaining time person–time contribution after past-use until end of follow-up.

Age- and sex-adjusted rate ratios with 95% CIs will be estimated for each of the three adverse outcomes comparing rivaroxaban with standard of care using Poisson regression analysis. Where numbers and data permit, adjustment will be made for relevant co-medication (described in the drug utilization section), indication and previous hospitalization for bleeding.

As a general strategy, no data imputation strategies will be applied to supplement missing data. The requirement for inclusion is complete data for critical variables such as exposure to rivaroxaban or standard of care and hospitalizations for bleedings or any other outcome event; otherwise this individual is not eligible to be a member of the study population. However, missing values may occur for potential confounder or effect modifying variables. In this case, individuals with missing values will be kept in the analysis and a separate category will be created for missing values of that variable. In sub-analyses to evaluate confounding or effect modification by variables with a large proportion of missing values, the evaluation will be considered to be conducted on the subset with complete data for the variable of interest.

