- use of other medications both in the year before the index date and following the index date: anticoagulants (including dabigatran etexilate and apixaban), antiarrhythmic drugs, antihypertensive drugs, statins, anti-diabetic agents, non-steroidal anti-inflammatory drugs, oral corticosteroids, acid-suppressive drugs, disease-modifying anti-rheumatic drugs, antidepressants, antipsychotic drugs, oral contraceptives, hormone-replacement therapy, strong inhibitors of either cytochrome P450 3A4 or P-glycoprotein (e.g. the systemic azole antimycotics ketoconazole, itraconazole, voriconazole and posaconazole and the HIV-protease inhibitor ritonavir), strong CYP3A4 inducers (e.g. rifampicin, phenytoin, carbamazepine or phenobarbital) and fluconazole. ✓
- renal status (estimated glomerular filtration rate [eGFR] or creatinine clearance [CrCl] to be obtained where available, and time of measurement relative to index date). Renal status to be defined as: normal renal function (CrCl > 80 mL/min); mild (CrCl < 80–50 mL/min), moderate (CrCl < 50–30 mL/min) or severe (CrCl < 30 mL/min) renal impairment and end-stage renal disease (CrCl < 15 mL/min) or requirement for dialysis). ✓
- smoking status and body mass index (BMI) recorded in the year before the index date and following the index date.
- hospital admissions for bleeding (see ICD-9 codes in Annex 3) in the year before the index date.
- healthcare utilization (e.g. hospital admissions) in the year prior to the index date. ✓

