9.3.2 Safety and effectiveness outcomes

For each outcome, potential cases will be identified using ICD-9-CM diagnostic codes ([Annex 3](#)) from hospital discharge diagnosis records.

For the purpose of this study, clinically relevant bleedings will be defined as bleedings leading to hospital admission. This restriction is needed to minimize differential misclassification caused by the variability in patients' behavior in seeking care for less severe bleedings. Similarly, the physicians'

attitude towards recording these events may differ between new drugs and standard of care. The consequence of restricting to bleedings identified through hospitalization or referrals is that bleedings leading to death before contact with a health care professional or hospital admission will be ignored. It is assumed that the number of bleeding events missed due to this restriction is small. Nevertheless, the magnitude and impact of this restriction will be assessed in another study of this PASS program (Swedish Record-linkage study).

9.3.2.1 Occurrence of intracranial haemorrhage, gastrointestinal bleeding and urogenital bleeding: case definitions

Intracranial haemorrhage (Annex 3, Table 4)

Cases of intracranial haemorrhage will be identified in patients admitted to the hospital that meet the criteria for one of the three following categories:

- incident cases of intracerebral haemorrhage recorded following or in association with computed tomography, magnetic resonance imaging (MRI) or x-ray angiography, or an appropriate therapeutic procedure.
- incident cases of subarachnoid haemorrhage recorded following computed tomography, MRI, X-ray angiography or lumbar puncture, or an appropriate therapeutic procedure.
- incident cases of epidural, dural, subdural and arachnoid haemorrhage recorded following computed tomography, MRI, x-ray angiography or lumbar puncture, or an appropriate therapeutic procedure.

As therapeutic procedures are not captured in the database, potential cases will be identified by hospital discharge diagnoses (ICD-9-CM). PHARMO will apply for chart review on therapeutic procedures to define the case (see [Section 9.4](#)).

Gastrointestinal bleeding (Annex 3, Table 5)

A patient will have to meet the following criteria to be considered a case of gastrointestinal bleeding:

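### Intracranial haemorrhage is defined as incident, but the counting rule has no look-back, so a bleed that preceded the index date can count as a new primary event

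*Protocol*

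**What the plan says.** **Case definition (Protocol 9.3.2.1).** All three intracranial categories are limited to incident cases; the first reads "incident cases of intracerebral haemorrhage recorded following or in association with computed tomography, magnetic resonance imaging (MRI) or x-ray angiography", and goes on to allow a therapeutic procedure instead. Because procedures are not in the database, candidates are found by discharge code (Annex 3, Table 4: 430, 431, 432), and "PHARMO will apply for chart review on therapeutic procedures to define the case".

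**Counting rule (Protocol 9.7.2).** The cohorts "will be followed up from the index date until 12 months after the end of the enrolment period". The event is then fixed by this sentence: "For each outcome, the first hospitalization for that outcome during the follow-up period will be identified".

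**Eligibility (Protocol 9.2).** Patients "registered in the database for at least 1 year before the index date will be included". An earlier bleed is not an exclusion.

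**Bleeding history.** Section 9.3.1 lists "hospital admissions for bleeding (see ICD-9 codes in Annex 3) in the year before the index date" as a baseline characteristic. Section 9.7.2 names previous bleeding admission as an adjustment variable, but only if the data are sufficient.

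**The concern.** The first admission in follow-up is not necessarily an incident event. Suppose a patient used a vitamin K antagonist before enrolment opened, is admitted under code 432, is then dispensed rivaroxaban for the first time, and is readmitted under 432 a few weeks later for the same bleed. Under 9.7.2 the readmission is the first coded admission in follow-up and counts as an intracranial haemorrhage on rivaroxaban. The same can happen in the comparator cohort, and to any patient in either cohort, switcher or not, who was admitted for such a bleed shortly before starting the index drug.

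At stake are the numerator of a primary rate ratio and the crude incidence rates of the primary outcomes, which Section 6 promises in both interim reports.

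**Working it through.** **1. Does anything else in the protocol make the count incident?**

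| Provision | What it does | Removes a carried-over bleed? |
|---|---|---|
| 9.2, one year of registration | Makes a look-back possible | No, none is applied |
| 9.3.2.1, 9.4, 9.8, chart review | Concerns procedures; needs approval from the register and each hospital | No |
| 9.3.1, 9.7.1, bleeding in the prior year | Describes and compares the cohorts | No |
| 9.7.2, adjustment for previous bleeding | Conditional covariate | No; the event stays in the numerator and in the crude rates |
| 9.7.2.2, sensitivity analyses | Vary the start and stop of treatment | No |

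**2. Who can be affected?** Section 9.1 assigns anyone who starts both drugs within enrolment to the cohort of the first one. A bleed on that first drug is then counted there, and a later readmission is not the first. What remains is patients with an intracranial admission shortly before index, including non-naïve patients whose comparator use predates enrolment. In the ACS group, earlier oral anticoagulant use is an exclusion.

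**3. The plan's own figure (4 Abstract, 9.5).** Inputs: 5 per 1000 person-years, 12,000 and 48,000 person-years, ratio to exclude 1.5, power 80%. Two-sided alpha of 0.05 is assumed, since 9.5 states none and the plan reports 95% intervals.

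- Expected events with no true difference: 0.005 × 12,000 = 60 and 0.005 × 48,000 = 240, total 300.
- Required events: (1.960 + 0.842)² / (0.2 × 0.8 × (ln 1.5)²) = 299, or 299 / 0.005 = 59,800 person-years, split 11,960 and 47,840.
- Power with 300 events: 80.2%.

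The stated size reproduces and is not in dispute. It refers to haemorrhagic stroke, so it serves below only as a scale for the wider intracranial outcome.

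**4. Effect on a null ratio.** Let fR and fV be the shares of counted events that are carried over in the rivaroxaban and comparator cohorts. The protocol gives neither, so a range is assumed. With equal true rates, observed ratio = (1 − fV) / (1 − fR).

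| fR | fV | Observed ratio (true 1) |
|---|---|---|
| 10% | 10% | 1.00 |
| 10% | 5% | 0.95 / 0.90 = 1.056 |
| 5% | 10% | 0.90 / 0.95 = 0.947 |
| 20% | 0% | 1 / 0.80 = 1.25 |
| 0% | 20% | 0.80 / 1 = 0.80 |

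**5. Effect on a true excess.** If carried-over bleeds are a share f of comparator events and occur at the same rate in both cohorts, a true 1.5 is seen as 1.5(1 − f) + f. This is 1.475 for f = 5%, 1.45 for 10% and 1.40 for 20%.

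**6. Information lost by removing them.** If a share f of the 300 events goes, power = Φ(√(300(1 − f) × 0.16) × ln 1.5 − 1.960), and the rivaroxaban person-years for 80% power are 11,960 / (1 − f).

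| f | Power | Rivaroxaban person-years for 80% |
|---|---|---|
| 2% | 79.4% | 12,204 |
| 5% | 78.2% | 12,589 |
| 10% | 76.0% | 13,289 |
| 20% | 71.0% | 14,950 |

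**The case against.** **The two sections can be read together.** The counting rule speaks of the outcome, and the outcome is defined as incident. The protocol is silent on history rather than saying that it is ignored, and window lengths are often left to an SAP. This stands in part. But the protocol itself fixes both the definition and the way events are counted, finds cases by code, and has no step that carries the restriction into the count.

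**The problem is narrow and partly visible.** The assignment rule in 9.1 removes most switching within enrolment, and prior bleeding admissions are tabulated. Both are true. They limit the number of cases and help to detect them, but remove none.

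**Stronger readings that the documents do not support.**

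- *A bias against rivaroxaban.* A reader might infer this because a bleed on one drug can prompt a change to another. Section 9.1 lets earlier users of either drug enter the opposite cohort, and carry-over needs no switch at all. No shares are given, so the direction is open.
- *A ratio of 1.10 to 1.20 with no true effect.* This follows if 0.5% to 1% of 12,000 users had a recent intracranial admission and 10% of these were readmitted: 6 to 12 extra events, 66/60 to 72/60. At 5 per 1000 per year, that prevalence equals one to two years of risk for every user, naïve users included, with no carry-over in the comparator. If instead 20% are switchers and the window is three months, 12,000 × 0.20 × 0.005 × 0.25 = 3 patients. A 10% readmission rate then gives 0.3 events and a ratio of 60.3/60 = 1.005; fivefold enrichment gives 1.5 events and 61.5/60 = 1.025. All of these are assumptions, and none can be preferred from the protocol.
- *The same mismatch for all primary outcomes.* The gastrointestinal and urogenital definitions do not ask for incident cases, so nothing is contradicted there.

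**Conclusion.** The point holds for intracranial haemorrhage only. The definition requires incident cases and the counting rule does not deliver them, so an admission or readmission for a bleed that preceded the index date can be counted as a new primary event. Nothing elsewhere in the protocol prevents this.

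Size and direction are unknown. Equal carry-over leaves a null ratio at 1.00 and dilutes a true excess; unequal carry-over moves the ratio either way. The assumed ranges only show that, in a study sized to exclude 1.5, modest shares could matter in either direction. The sample size itself is not called into question. This should be settled before the outcome analysis, because the repair is simple and a later choice of look-back could be influenced by the data.

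**What to change.** In 9.7.2, define an incident intracranial haemorrhage as one in a patient with no hospital admission under a Table 4 code in the year before the index date. Remove patients with such an admission from that outcome's risk set in both cohorts, events and person-time alike; removing events alone would understate the rates. Report the unrestricted count as a sensitivity analysis. For gastrointestinal and urogenital bleeding, apply the same look-back as a sensitivity analysis only.

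The cost is a sentence or two and one query. Every patient has at least a year of registration (9.2), and the pharmacy database is fully linked to the hospital register (9.4), so the look-back does not depend on GP data. If ICD-10 codes are added as 9.4 foresees, the look-back must use them too. The price is that a small number of high-risk patients and some true early rebleeds leave the main intracranial analysis, with the loss of power shown above. The look-back does not settle the in-hospital starters of 9.7.2.1, where bleed and first dose can fall in one admission; their order would have to come from the chart review that section makes conditional.
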